### 7.8 Discontinuation of the Study

The Sponsor may terminate the study at any time for any reason. Subjects would still be followed for safety. In the event the study is terminated, the IECs and appropriate regulatory authorities will be notified of the decision.

### 8. SUBJECT SELECTION

### 8.1 Source of Subjects and Recruitment Methods

Following appropriate Human Studies review and approval (see Section 15), the Investigator may initiate and manage subject recruitment. To reach an economically and socially diverse population, the study may be announced in newspapers and on relevant Internet websites.

#### 8.2 Subject Disclosures and Restrictions during the Conduct of the Study

This is a Phase 1 study of healthy subjects and subjects with HIV infection. In the interest of their safety and to facilitate accurate assessment of the data, the subjects will agree to the disclosures and restrictions detailed in Table 8-1 for the duration of their participation in the study, i.e., screening visit to End-of-Study (EOS) visit.

Table 8-1. Subject disclosures and restrictions during the conduct of the study

Item / Activity	Action	Comment
Prescription medication	Disclosure	Prescription medications in use at the time of screening will be reviewed in detail. Medications subsequently prescribed by physicians other than the Investigator will be disclosed promptly.
Over-the-counter medication	Disclosure	Over-the-counter medications in use at the time of screening will be reviewed in detail. Over-the-counter medications subsequently initiated by the subject will be disclosed promptly.
Herbal products a	Prohibited	Patients will be instructed about the range of products containing St. John's Wart and other herbals.
High-dose Vitamins ⁵	Prohibited	Vitamins and minerals in doses substantially exceeding recommended daily requirements.
Blood donation	Prohibited	-

a. Patients will be instructed about the range of products containing St. John's Wart, other herbals, caffeine or xanthines (including chocolate).

b. Vitamins and minerals in doses substantially exceeding recommended daily requirements.

#### 8.3 Definitions

### 8.3.1 Non-childbearing potential

Non-childbearing potential is defined as meets one of the following two criteria:

- documented hysterectomy or bilateral oophorectomy.
- age  $\geq$ 50 years, no menses for at least 3 years, **and** post-menopausal FSH level;

### 8.3.2 Effective birth control (contraception) methods

Effective birth control (contraception) methods means strict abstinence or use of *two* of the following methods: hormonal contraceptive (oral, injectable, implanted [e.g., ImplanonTM], or intravaginal ring), condom, diaphragm, spermicide, or an intra-uterine device.

#### 8.4 Subject Selection Criteria

Subject selection criteria are detailed in Section 2.4, including

- Inclusion and Exclusion Criteria HIV-negative Subjects (Sections 2.5.1 and 2.5.2, respectively)
- Additional Inclusion / Exclusion Criteria for HIV-positive Subjects (Section 2.5.3 and 2.5.4)

### 8.4.1 Observed Variances

Subjects meeting inclusion and exclusion criteria at screening may be scheduled for enrollment. If on Day 1 prior to the first dose, clinical variances are noted compared to screening enrollment may proceed with the approval of the Medical Monitor.

**Confidential and Proprietary** 

[name] 5/31/15 10:25 AM **Deleted:** 15

[name] 5/31/15 10:25 AM Deleted: Table 8-1

Page 38 of 75 Date: 30 March 2015

### 9. STUDY TREATMENTS

#### 9.1 Study Treatments to be Administered

#### Table 9-1. Study treatments

Role in Study	Identity of treatment	Comments
Investigational	DAR-901	Administered by ID injection
Active Comparator	Tice BCG	Organon, Teknika, 0.1 mL intradermal, diluted to 1-8 x 10  CFU
Placebo Control	Sterile Saline for Injection	Administered by the same route and in the same dose volume.

#### 9.2 Identity of the Investigational Product

#### Table 9-2. Physical and Chemical Properties of Active Ingredient (Drug Substance)

Name	DAR-901
Vaccine Class	whole-cell, heat-killed organisms
Appearance	Slightly turbid yellow suspension

#### Table 9-3. Formulation of DAR-901 for Injection (Drug Product)

Name	DAR-901 for Injection
Active ingredient	DAR-901
Excipients	Borate-buffered 0.9% NaCl
How supplied	Sterile 2 mL vial containing 0.35 ± 0.05 mL of 10 mg/mL DAR-901
Storage	2-8°C
Preparation and handling	Preparation varies by dose level; see Section 9.3 for details.
Administration	The dose is administered as a single intradermal (ID) injection in the deltoid using a fresh sterile needle (approximately 26g).

#### Table 9-4 Formulation of Tice BCG for Injection (Positive Control)

Name	Tice BCG
Active ingredient	M. bovis, BCG
How supplied	Freeze dried preparation in vial containing 1-8 x 10  CFU BCG
Storage	2-8°C
Preparation and handling	Reconstituted with sterile water to achieve concentration of 1-8 x 10  CFU BCG/0.1mL
Administration	The dose is administered as a single intradermal (ID) injection in the deltoid using a fresh sterile needle (approximately 26g).

### 9.3 Preparation and Handling of DAR-901 for Injection by Dose Level

#### 9.3.1 0.1 mg DAR-901 for Injection

- Gently agitate the vial (0.3-0.4 mL at 10mg/mL) to assure an even suspension.
- Withdraw 0.22 mL from the vial.
- Add 0.22 mL to a 2 mL vial of Sterile Saline for Injection, USP.
- Gently agitate the vial to assure an even suspension.
- Withdraw 0.1 mL from the vial for administration.

### 9.3.2 0.3 mg DAR-901 for Injection

- Add 0.65 mL of Sterile Saline for Injection, USP to the vial.
- Gently agitate the vial to assure an even suspension.

- Withdraw 0.1 mL from the vial for administration.

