# 2.4.1 Enrollment Process

As part of the overall risk management plan (see below for additional provisions), enrollment will proceed as follows:

- The study will start with dose group A1 (HIV-negative, IGRA-negative; 0.1 mg per dose).
  - The enrollment procedure comprises the following steps:
  - The first subject will be dosed with vaccine (Day 1) open-label, observed for 1 hr, and examined on Day 3 (~48 hr post-dosing). If there have been no significant safety-related events, enrollment will proceed.
  - For the remaining 15 subjects in the dose group, treatment will be assigned by randomization for A1-A3 and will be open label for A4, B1 and B2
  - A maximum of five subjects may be randomized per calendar day.
- After all subjects in the dose group have completed Study Day 7 follow-up visit, all available data will be reviewed by the Dose Review Committee (DRC; see Section 7.7 for details). Escalation to the next dose level will be contingent on their recommendation.
- If the DRC approves dose-escalation, then enrollment in dose group A2 will commence, using the same process as described for group A1. Similarly, a dose-escalation review will be conducted after all group A2 subjects complete Day 7 follow-up visit; and, if approved, enrollment in dose group A3 will proceed as detailed above.
- After all subjects in dose group A3 have completed the 7d safety evaluation after dose #3 the available safety data including injection site reactions will be conducted by the DRC, supplemented by the PI and, possibly, additional consultants with relevant expertise (e.g., immunology, tuberculosis).
- If the DRC concludes that the A3 dose level of 1 mg is safe then dose group A4 (HIV-negative, IGRA-positive) will be enrolled and administered the 1 mg dose level. If the DRC determines that the 1 mg dose is not safe then they will recommend one of the lower dose levels from A1 or A2 for A4. Subjects may be enrolled as available, up to a maximum of four subjects per calendar day.
- The dose selection review will also assess the vaccine's safety with regard to its administration to HIV-positive subjects. Progression to Part B will be contingent on that review and on the availability of resources.
- Dose group B1 will comprise HIV-positive, IGRA-negative subjects scheduled to receive DAR-901 at the same dose as the A4 cohort. This dose group will be enrolled using the same dose procedure steps detailed above for dose group A4.

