### 2.4.4 Potential protocol adjustments

The protocol is written with flexibility to accommodate the dynamic nature of Phase 1 clinical trials. An additional cohort may be enrolled, either to repeat a dose level or to administer a dose below or between the levels specified. In no event will the proposed maximum exposures be exceeded.

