# 2.8 Statistical Analyses

#### 2.8.1 Analysis Populations

Within each population (HIV-negative and –positive), analyses will be performed comparing subjects by dose level and by treatment assignment (DAR-901 vs. Placebo). Where appropriate, data for different dose levels may be pooled.

- Safety Population all subjects who received at least one injection of study medication.
- *Immunogenicity Populations* all subjects with evaluable immunogenicity data, based on protocol compliance, adequate numbers of samples, and successful sample assays.

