### 9.3.3 1 mg DAR-901 for Injection

- Gently agitate the vial to assure an even suspension
- Withdraw 0.1 mL from the vial for administration.

Detailed dose-preparation instructions and flow-sheets will be provided in the Pharmacy Manual.

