### 14.3 Statistical Methods

Study results will be analyzed using descriptive statistics. Adverse events will be listed per dose level and analyzed by intensity and relationship to investigational product. All other variables will be analyzed descriptively per dose level. No formal statistical comparisons are planned.

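### The section 9.3.2 recipe for the 0.3 mg level gives about 0.35 mg (0.32 to 0.38 mg), so A2 would be reported under the wrong dose

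*Protocol*

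**What the plan says.** Table 9-3 describes the drug product as "Sterile 2 mL vial containing 0.35 ± 0.05 mL of 10 mg/mL DAR-901". Section 9.3.1 repeats that fill and strength in the first step of the 0.1 mg recipe: "Gently agitate the vial (0.3-0.4 mL at 10mg/mL) to assure an even suspension".

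Section 9.3.2 covers the 0.3 mg level. Its first step is "Add 0.65 mL of Sterile Saline for Injection, USP to the vial". Nothing is withdrawn beforehand. The vial is then agitated and 0.1 mL is taken for injection. Section 9.3.3 takes 0.1 mL undiluted for the 1 mg level, and adds: "Detailed dose-preparation instructions and flow-sheets will be provided in the Pharmacy Manual".

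The levels matter in three places:

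- **Reporting.** Section 14.3 lists adverse events per dose level and says of the rest: "All other variables will be analyzed descriptively per dose level". Section 2.8.1 adds: "Where appropriate, data for different dose levels may be pooled".
- **Dose selection.** If the Dose Review Committee finds 1 mg unsafe, section 2.4.1 says "they will recommend one of the lower dose levels from A1 or A2 for A4". B1 and B2 take the same dose as A4.
- **Extra cohorts.** Section 2.4.4 says: "An additional cohort may be enrolled, either to repeat a dose level or to administer a dose below or between the levels specified".

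**The concern.** The whole vial is diluted, so the concentration depends on how much suspension the vial holds. With 0.35 mL at 10 mg/mL, 0.65 mL of saline makes exactly 1.00 mL at 3.5 mg/mL. The 0.3 mg label needs 3 mg/mL.

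This is a dose-ranging trial with three levels, and dose level is the unit in which safety and immunogenicity are described. A wrong middle dose puts A2's results at the wrong point on the dose scale and alters the two dose steps. It also matters if the A2 level is used again: a later cohort given a true 0.30 mg would not receive what A2 received.

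The recipe also lets the dose vary with the fill. The other two recipes do not, because one transfers a fixed 0.22 mL and the other injects undiluted suspension.

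**Working it through.** **Inputs.** Fill 0.30, 0.35 (nominal) or 0.40 mL and strength 10 mg/mL (Table 9-3, section 9.3.1); saline 0.65 mL (section 9.3.2); injected volume 0.1 mL (sections 9.3.1 to 9.3.3). Volumes are taken as additive.

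**Formula.** Dose = 0.1 mL × (volume of suspension × 10 mg/mL) ÷ (volume of suspension + saline).

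**Check on the other two levels.**

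- 0.1 mg: 0.22 mL into 2 mL gives 2.2 mg ÷ 2.22 mL × 0.1 mL = 0.099 mg.
- 1 mg: 10 mg/mL × 0.1 mL = 1.00 mg.

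Both agree with their labels within 1%.

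**The 0.3 mg level.**

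| Fill (mL) | Drug (mg) | Final volume (mL) | Dose in 0.1 mL (mg) | Against 0.30 mg |
|---|---|---|---|---|
| 0.30 | 3.0 | 0.95 | 0.316 | +5.3% |
| 0.35 | 3.5 | 1.00 | 0.350 | +16.7% |
| 0.40 | 4.0 | 1.05 | 0.381 | +27.0% |

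The labelled figure is not reproduced. The fill at which 0.65 mL of saline would give 0.300 mg is 0.65 ÷ (10/3 − 1) = 0.279 mL, below the permitted minimum of 0.30 mL. The error therefore runs upward at every permitted fill. Between the extremes, 0.381 ÷ 0.316 = 1.21, so two A2 injections with the same label could differ by about 21%.

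**Other readings.**

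- Section 5.3.2 gives the strength of the same 0.3 to 0.4 mL fill as 1 mg/mL. That would make the A2 dose 0.032 to 0.038 mg, and the other two recipes would also miss their labels tenfold. The 10 mg/mL figure is the one the recipes assume.
- Reading 0.65 mL as the final volume gives 0.1 × 3.0/0.65 = 0.46 mg to 0.1 × 4.0/0.65 = 0.62 mg.

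Neither reading gives 0.30 mg.

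**Consequences if the recipe is followed.**

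- Three-dose exposure: 3 × 0.350 = 1.05 mg (0.95 to 1.14 mg) against 0.90 mg as labelled.
- Step from A1 to A2: 0.350 ÷ 0.0991 = 3.5-fold (3.2 to 3.8) against 3.
- Step from A2 to A3: 1 ÷ 0.350 = 2.9-fold (2.6 to 3.2) against 3.3.
- Mean dose if the 30 DAR-901 subjects of A1 to A3 are pooled: (0.0991 + 0.350 + 1) ÷ 3 = 0.483 mg against (0.1 + 0.3 + 1) ÷ 3 = 0.467 mg, or +3.5% (+1.1% to +5.7% over the fill range).

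**The case against.** The best case on the other side accepts the arithmetic and disputes its weight.

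- **The Pharmacy Manual holds the detailed instructions.** It is not shown and may give a different volume. This stands as a condition: the protocol alone cannot show what was injected. But if the Manual differs, the two documents conflict and section 9.3.2 still needs correcting.
- **The practical effect is small.** The dose stays below the 1 mg maximum, the escalation order holds, and the levels remain roughly threefold apart. There are 10 DAR-901 subjects per level and no formal comparisons, so no test, threshold or power figure depends on exactly 0.30 mg. The mouse data behind the 0.3 mg level come from a coarse dose grid (0.1, 0.3, 1.0 mg around the peak) that cannot separate 0.30 from 0.35 mg. All of this stands, and it limits the seriousness of the point.
- **Reuse as a fallback largely cancels out.** An unchanged recipe would give A4, B1 and B2 the dose A2 actually had, so only the label would be wrong. This also stands. A real mismatch arises only if the recipe is changed after A2 has been dosed, and the fix has to guard against that.

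**Conclusion.** The concern holds. As written, section 9.3.2 does not deliver its labelled dose at any permitted fill. It gives 0.350 mg at nominal fill, 17% too much, with a range of 0.316 to 0.381 mg (+5% to +27%). If the recipe is followed, results reported at 0.3 mg belong to about 0.35 mg.

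This rests on a strength of 10 mg/mL, fills within 0.30 to 0.40 mL, additive volumes, and preparation according to the protocol text. The point should be fixed because a stated dose is wrong in a dose-ranging trial. It does not threaten the dose cap, the escalation sequence or the form of the analysis, and its effect on any pooled DAR-901 summary is small.

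**What to change.** First check the A2 pharmacy preparation records. The protocol does not say whether A2 has been dosed.

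1. **No A2 subject dosed.** Replace the recipe with a fixed transfer: withdraw 0.21 mL of suspension, add it to 0.49 mL of Sterile Saline in an empty sterile vial, agitate, and inject 0.1 mL. This gives 2.1 mg ÷ 0.70 mL × 0.1 mL = 0.300 mg at every fill. Section 9.3.1 already withdraws 0.22 mL from the same vial, so the volume is available; the pharmacist should confirm the handling. A simpler change is 0.82 mL of saline in place of 0.65 mL. That gives 0.299 mg at nominal fill but leaves 0.268 to 0.328 mg (−11% to +9%) across fills.
2. **Any A2 subject dosed by the present recipe.** Do not change the preparation within A2 or for any cohort that reuses the A2 level. A cohort switched to 0.30 mg would receive 1 − 0.30/0.35 = 14% less per dose than A2 did. Restate the level as about 0.35 mg (0.32 to 0.38 mg) in the protocol and the dose-level summaries. Keep a corrected recipe for a new cohort under section 2.4.4 that is meant to receive a true 0.30 mg.
3. **Records show another recipe.** Put that recipe in section 9.3.2 and label A2 by the dose it gives.

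Align the Pharmacy Manual in each case, and correct the 1 mg/mL in section 5.3.2 in the same revision.

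The cost is a check of records, then one recipe line or one dose label, plus the strength correction, made as a protocol revision under section 16.2 with the usual ethics and regulatory approval. Sample size, visits and analysis methods do not change.

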### 9.3.3 1 mg DAR-901 for Injection

- Gently agitate the vial to assure an even suspension
- Withdraw 0.1 mL from the vial for administration.

Detailed dose-preparation instructions and flow-sheets will be provided in the Pharmacy Manual.

#### 9.4 Reference and Blinding Therapy

Tice BCG is used as the active comparator. Sterile Saline for Injection is used as the placebo control and for blinding (i.e., the first and second injections in BCG subjects).

### 9.5 Administration of Study Treatments

Each dose of DAR-901, BCG or placebo will be administered as a single intradermal (ID) injection. The recommended site for injection is the upper deltoid region of the arm, with sequential doses administered in the opposite arm. In the event this recommendation cannot be accommodated due to injury or other issue, the same arm may be used successively, placing the injection at least 5 cm apart.

### 9.5.1 Variances in Dose Administration Schedule

The protocol permits variance in dose administration of plus or minus seven (7) days from the nominal scheduled timepoint. Variances that would exceed plus or minus seven (7) days should be discussed with the Medical Monitor.

### 9.6 Method of Assigning Patients to Treatment Groups

The first subject in dose group will be assigned active treatment (DAR-901)(see Section 2.4.1). For subsequent subjects within the dose group treatment will be assigned by computer-generated randomization for A1-A3 and open label for A4, B1 and B2. Suitable randomization procedures will be established by the CRO data management and clinical services performing the protocol and approved by the Sponsor. The research pharmacist will be provided a list of treatment assignments.

### 9.7 Selection of Dose Levels in the Study

See Section 7.2.1.

### 9.8 Selection of Dose Number and Interval

See Section 7.2.2.

### 9.9 Blinding

Subjects randomized to placebo regimen will receive an injection of Sterile Saline for Injection at the same dose volume as active treatment. The pharmacist is responsible for maintaining the blind, that is, assuring that treatment allocation is not revealed to other study staff or the patients.

#### 9.9.1 Procedures for Unblinding Individual Patients during the Study

There are no specific treatments for the effects of DAR-901; the Investigator should manage patients symptomatically based on any changes observed. Consequently, it is not expected that the treatment allocation for a particular subject will need to be revealed (i.e., unblinded).

If the Investigator needs to unblind the treatment assignment for a particular subject, prior approval by the Medical Monitor should be obtained and the following information entered into the medical record:

- date and time of the last injection,
- reasons study drug was discontinued,
- name of the Medical Monitor who approved unblinding,
- reasons the subject's treatment allocation was unblinded.

In the event of a true medical emergency in which the Investigator judges that the subject cannot be managed safely without unblinding, the Investigator may obtain the treatment allocation directly from the

pharmacist at the site. All steps above will be followed, including contacting the Medical Monitor as soon as possible and not more than 24 hours afterwards.

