#### 2.4 Study Design

This is a Phase 1, randomized, controlled, double-blind, multiple-dose, dose-ranging study of DAR-901 to be conducted in HIV-negative and HIV-positive adults previously vaccinated with BCG. The goals of the trial are to determine the safety, tolerability, and immunogenicity of multiple doses of the vaccine at different dose levels, ranging from 0.1 to 1 mg. The maximum dose level (1 mg) corresponds to the dose of SRL 172 used in the successful DarDar trial. A dose of 0.3 mg DAR-901 provided maximal immunogenicity in mice; the 0.1 mg dose is included to provide further dose response data and assure a safe starting dose level.

Doses will be administered by intradermal injections in the deltoid area at 0, 2, and 4 months (Day 1, Day 53-67, and Day 113 to 127, respectively). In the Phase 2 study of SRL 172 conducted in Finland, this regimen showed significant immunogenicity. The intervals between injections and route of administration are consistent with all previous studies of SRL 172.

Table 2-1, displays the dose groups by HIV status and dose level (mg) per injection. All cohorts include placebo (saline) controls; in addition, the HIV-negative cohorts (A1–A3) include positive controls (a single dose of BCG as Dose #3, with saline at preceding doses).

[name] 5/31/15 10:25 AM **Deleted:** Table 2-1

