### 12.5 Sponsor Guidance for Grading of Injection Site Reactions

As detailed in Section 5.5, the adverse events associated with intradermal injection of SRL 172 were primarily injection site reactions similar to, but generally milder than, reactions to BCG vaccination, which has been used world-wide for over 70 years. Further, DAR-901 is a heat-inactivated vaccine with no living organisms, so the rare invasive BCG complications of lymphangitic or hematogenous spread are not under consideration, even in HIV-infected persons.

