### 12.5.3 Definitions of the Most Commonly Expected Injection Site Findings

- Erythema: reddening of the skin.
- Desquamation: skin coming off in scales, often patchy or circumferential; maximum linear diameter will be recorded only if the area of involvement is a continuous patch.
- Induration: an area of skin that is thicker, firmer than usual. Will be used to include both the related terms papule / nodule (a solid raised lesion with distinct borders, <1 cm diameter) and plaque (papule-like lesion, >1 cm), since diameter will be recorded independently.
- Vesicle / Blister: a sub-epidermal collection of clear fluid
- Pustule: a sub-epidermal collection of white or yellow fluid up to 2.5 cm diameter that based on appearance is presumed to be "pus", i.e., to contain neutrophils. Commonly seen after intradermal injection of BCG or heat-killed mycobacteria, but rarely infected with pyogenic bacteria.
- Erosion: the loss of the surface of the skin; typically results in a shallow moist or crusted lesion. In the studies with SRL 172 (see Section 5.5), this process was reported as "skin breakdown".

- Ulceration: full thickness loss of epidermis, with erosion into dermal or deeper tissue; commonly crusted or with granulation.
- Crust: dried material covering an erosion or ulceration; may be white or colorless if composed of plasma or exudate, or darker if small amounts of blood are present.
- Eschar: hard dry plaque covering an ulcer, implying underlying tissue necrosis
- Abscess: a sub-epidermal collection of white or yellow fluid greater than 2.5 cm diameter that based on appearance is presumed to be "pus", i.e., to contain neutrophils. If closed, the lesion is typically fluctuant, that is yields to palpation consistent with containing fluid. Abscesses may open and drain spontaneously or may be incised and drained by the investigator. Abscesses will be classified as "Sterile" or "Infected (Pyogenic)" (see below).
  - If an abscess is incised by the investigator, a fresh culture should be obtained. Open lesions
    have a high likelihood of contamination and culture is generally only useful if there are other
    findings, such as surrounding cellulitis or acute systemic symptoms.
  - The investigator may prescribe topical or systemic antibiotics based on their judgment of the risk of current or potential pyogenic involvement. The expected pathogens would be *Staphylococcus aureus* or β-hemolytic streptococci.

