- Sterile Abscess: In a recent prospective, active surveillance of BCG immunization, sterile abscess was reported in 3.6% (18/504) persons over 6 months of age [18]. In the DarDar trial, sterile abscess was observed in 0.3% of HIV-infected adults who received SRL 172 [1]. Neither study reported any pyogenic abscesses. Sterile abscesses are typically not accompanied by surrounding erythema, warmth, or marked tenderness, or by fever or regional lymphadenopathy [19].
- Infected Abscess: An abscess due to pyogenic bacteria, typically *Staphylococcus aureus*. In addition to documented positive cultures, pyogenic abscess is expected to be accompanied by at least one of the following: surrounding erythema, warmth, or marked tenderness. Infected abscess also often present with fever and regional lymphadenopathy.
- Scar: an area of fibrous tissue that replaces normal skin after injury; a natural sequela of wound repair and healing. Often associated with mild discoloration.

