### 12.5.4 Visit Assessment of Injection Site Reactions and Other Post-Dosing Events

At each visit specified in Sections 2.9 and 12.2, the subject will have vital signs obtained, be interviewed by study personnel regarding symptoms and other events, and examined by the Investigator.

Treatment-emergent changes in vital signs will be graded using the criteria shown in Table 20-2, which are taken from FDA Guidance [20].

Subjects will be explicitly asked about systemic and local symptoms (see Sections 12.5.1 and 12.5.2, respectively), any interference with daily activities, and any treatment required. Symptoms will be graded using the functional criteria shown in Table 12-4.

Investigator will examine all of the prior injection sites and then:

- Record the presence or absence of the physical findings defined in Section 12.5.3;
- For any findings present, record the maximum linear diameter in mm;
- Pain, erythema, and induration will be graded as shown in Table 12-5, taken from FDA Guidance [20]; other ISRs characteristics will be graded using the functional criteria shown in Table 12-4.
- Considering *all* the findings present, the investigator grade the *overall* intensity (severity) of the ISR as per Table 12-4.
- This grade should be "static", that is, based upon the impact and management of the ISR at the time, without reference to previous observations for the subject.
- Subjects will be asked for permission to photograph the ISR if it is assessed as Grade 2 or higher, is accompanied by systemic symptoms, or is managed with prescription medication (e.g., systemic antibiotics or prescription analgesics). Photographs are completely optional and may be declined by the subject without impacting any other aspects of the protocol.

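### Sections 9.9.1 and 12.5 argue from killed DAR-901 alone on unblinding and invasive spread, although 9 of 45 blinded A1-A3 subjects receive BCG at Dose #3

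*Protocol*

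**What the plan says.** Section 2.4 says that cohorts A1-A3 "include positive controls (a single dose of BCG as Dose #3, with saline at preceding doses". Table 2-1 gives each of these cohorts 10 DAR-901, 3 BCG and 3 placebo subjects. Tables 9-1 and 9-4 specify the BCG dose in colony-forming units. Under section 2.4.1 the first subject in each cohort receives DAR-901 open-label. After that, "For the remaining 15 subjects in the dose group, treatment will be assigned by randomization for A1-A3". Section 2.4.2.2 has blinded staff give the injections and make the evaluations in these cohorts.

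Section 9.9.1 opens its unblinding procedure with "There are no specific treatments for the effects of DAR-901; the Investigator should manage patients symptomatically based on any changes observed" and continues: "Consequently, it is not expected that the treatment allocation for a particular subject will need to be revealed". It then provides two routes. One is unblinding with the Medical Monitor's prior approval. The other is direct access through the site pharmacist in a medical emergency.

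The opening of section 12.5 says: "DAR-901 is a heat-inactivated vaccine with no living organisms, so the rare invasive BCG complications of lymphangitic or hematogenous spread are not under consideration". Section 12.5.3, within the same guidance, does draw on BCG experience for local findings. Of pustules it says "Commonly seen after intradermal injection of BCG or heat-killed mycobacteria", and it cites a sterile-abscess rate of 3.6% (18/504) from BCG surveillance.

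**The concern.** Both statements start from a property of DAR-901 and end in guidance that covers every blinded subject. In 9.9.1 the absence of a specific treatment for DAR-901 effects leads to symptomatic care and to an expectation about unblinding "a particular subject", whatever that subject received. In 12.5 the absence of living organisms in DAR-901 is the only ground for setting aside invasive spread. The protocol itself calls that spread a BCG complication, and the trial gives BCG.

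The situation at stake is narrow. After Dose #3, a blinded investigator may suspect invasive spread in an A1-A3 subject. The guidance tells that investigator that this complication is not in question and that breaking the code is not foreseen. Yet one blinded subject in five was assigned BCG. The plausible harm is delay or under-recognition in a trial whose primary objective is safety.

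**Working it through.** **Blinded subjects and BCG recipients** (Table 2-1 and section 2.4.1)

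- Enrolled in A1-A3: 3 × 16 = 48.
- Open-label first subjects, all on DAR-901: 3 × 1 = 3.
- Randomized and blinded: 48 − 3 = 45, which agrees with 3 × 15.
- By arm: DAR-901 30 − 3 = 27; BCG 3 × 3 = 9; placebo 3 × 3 = 9. Check: 27 + 9 + 9 = 45.
- BCG share of blinded subjects: 9/45 = 20%.
- BCG share of blinded subjects given an active product at Dose #3, with no dropout: 9/(27 + 9) = 25%.

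**Reach of each statement**

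| Section | Ground given | Guidance drawn | Does the ground cover BCG recipients? |
|---|---|---|---|
| 9.9.1 | No specific treatment for DAR-901 effects | Symptomatic care; unblinding not expected for a given subject | No, it concerns DAR-901 only |
| 12.5, opening | DAR-901 contains no living organisms | Invasive BCG complications set aside | No, BCG is dosed in colony-forming units |
| 12.5.3 | BCG and killed-mycobacteria experience | Descriptions of local findings | Yes |

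The gap is therefore confined to invasive spread and to the stated reason for not expecting unblinding. Before Dose #3 the BCG subjects have had only saline, so the gap opens at Dose #3.

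**Chance that the situation arises**

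The protocol calls the invasive complications rare and gives no rate, so the rates p below are assumptions. P(at least one in 9) = 1 − (1 − p)^9.

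| Assumed p per BCG recipient | P(at least one in 9) |
|---|---|
| 0.01% | 0.09% |
| 0.1% | 0.9% |
| 1% | 8.6% |

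**Why isolated adenopathy should not trigger unblinding**

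Table 5-4 (Study 005, HIV-positive subjects) reports adenopathy in 5% after each dose, with SRL 172 and with control alike. Carrying 5% over to the 27 + 9 = 36 blinded subjects not given BCG is an assumption, so a range of 1% to 10% is shown.

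| Assumed p | Expected cases, 36p | P(at least one), 1 − (1 − p)^36 |
|---|---|---|
| 1% | 0.36 | 30% |
| 5% | 1.8 | 84% |
| 10% | 3.6 | 98% |

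Adenopathy alone would probably occur in at least one subject who never had BCG, so using it as a trigger would break codes for no benefit.

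**The case against.** The strongest reply is that both sentences are true as written. Section 9.9.1 speaks of DAR-901 effects, and "not expected" is a forecast rather than a bar; at the lower assumed rates the forecast is accurate. The sentence in 12.5 goes on to mention HIV-infected persons, who receive no BCG in this trial, so it is a statement about DAR-901. This stands as a reading of intent. It does not remove the difficulty, because 9.9.1 extends its conclusion to any subject and 12.5 is the grading guidance used for BCG recipients too. By their own logic, the grounds stop short of that arm.

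The second reply is that the event is already provided for, and this stands in full. A possibly related systemic event of Grade 2 or higher lasting more than 48 hours is a dose-limiting toxicity, for which 7.5.1 permits unblinding. Serious events go to the Dose Review Committee, which may ask to be unblinded (7.7). Section 9.9.1 has its own two routes, and 12.3.6 has adverse events investigated for cause.

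A reader might go further in four ways that the documents do not support:

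- **That unblinding of BCG recipients is barred or unprovided for.** The routes above apply to them.
- **That 12.5 overlooks BCG altogether.** Section 12.5.3 uses BCG experience for local reactions.
- **That symptomatic care is wrong because BCG disease has a specific treatment.** The protocol does not say so, and this point does not rely on it. The point is that the reason given does not extend to BCG.
- **That regional lymphadenopathy must be added as a recorded finding.** It is true that at visits the investigator must "Record the presence or absence of the physical findings defined in Section 12.5.3", and that 12.5.3 mentions nodes only when describing abscesses, as in "Infected abscess also often present with fever and regional lymphadenopathy". But a regional node is not an injection-site finding. New examination findings are recorded under 10.1, and 12.2 adds scripted and open-ended questions about adverse events. The sign is non-specific, and a comparison with 9 BCG recipients would tell little. Recording it at late visits would override the 12.2 rule that only serious events with onset after day 28 are recorded, and it would correct neither sentence.

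**Conclusion.** The point holds as a fault of rationale. Two statements that guide the care of blinded subjects rest solely on properties of killed DAR-901, while 9 of 45 blinded A1-A3 subjects (20%) receive BCG at Dose #3. The counts follow from the protocol and assume no dropout or replacement. The clinical consequence is limited to possible delay or under-recognition of invasive spread. Its absolute probability is small: 0.09% to 8.6% for at least one event, over assumed rates of 0.01% to 1%, and the top of that range sits uneasily with the protocol's description of these events as rare. No analysis or sample-size figure is affected. The change is optional but worth making, because it costs almost nothing and bears on subject safety.

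**What to change.** 1. **Section 12.5:** state that the exclusion of lymphangitic and hematogenous spread applies to DAR-901 recipients and not to BCG recipients.
2. **Section 9.9.1:** limit the reasoning on symptomatic care and unblinding to DAR-901. Add that after Dose #3 a blinded A1-A3 subject may have received BCG. Name suspected invasive BCG spread as a recognised reason to request unblinding through the existing Medical Monitor or emergency route, and say that isolated adenopathy is not such a reason.

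The cost is two wording edits and possibly a rare extra code break. No new visit, assessment, form line or unblinding route is needed.
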